4.1.5. OTHER DERIVATIONS

No other derivations besides PRO endpoints will be described in this analysis plan.

To calculate time interval duration, a month is 30.4375 days and a year 365.25 days.

4.2. PRO VARIABLES

4.2.1. CARES CORVIDIA ePRO

For each item, weekly scores will be derived as the average of the 7 consecutive daily scores as follows:

- Baseline = average of Day -7 to Day -1
- Week 5 (Visit 4) = average of Day 22 to Day 28
- Week 13 (Visit 7) = average of Day 78 to Day 84
- Week 24 (Visit 11) = average of Day 155 to Day 168

For Baseline, Week 5 and Week 13, if more than 3 daily scores out of the 7 days (>50%) within the weekly period are missing, then the score is set to missing.

For Week 24, if more than 7 daily scores out of the 14 days (>50%) within the bi-weekly period are missing, then the score is set to missing.

Document: \\ieedc-vnasc01\Sites\ [REDACTED]\NLHOF\IntProjects\Consulting\Projects\ Corvidia\ [REDACTED]\Biostatistics\01.Documentation\02.SAPI Corvidia_RESCUE_PROSAP_v2.0_21JUL2020
Author: [REDACTED] Version No: v.2.0
Template No.: [REDACTED] Version Date: 21JUL2020
Effective Date: 01Dec2018 Reference: [REDACTED]

Preliminary scoring of the CARES includes the calculation of a Total Symptom Score (TSS). Alternative means of scoring the CARES will be explored in a separate psychometric analysis plan (PAP) and if any derived, these will be included in this SAP for efficacy analysis. Additional scales and subscales may be derived based on the results of the psychometric analysis plan (PAP). A higher score for the TSS or other scales/subscales represent more symptoms.

Change from baseline defined as post-baseline value minus baseline value will be calculated for each assessment. At each post-baseline assessment, the change in score from baseline will be calculated for each scale/item.

Domain scores may result from the psychometric analyses described in a separate PAP. In this PAP, clinically meaningful thresholds for these potential domains will also be derived. Change from baseline in the TSS score, as well as the domain scores that may result from the psychometric analysis, will be categorized at each visit as improvement/stable/deterioration using the clinically meaningful threshold value for change scores derived in the psychometric analyses as follows:

- Improvement: a change from baseline \leq -threshold points;
- Deterioration: a change from baseline \geq threshold points
- No change: a change from baseline between (-threshold to threshold).

Sensitivity analyses may be performed if more than one threshold values are suggested by the psychometric analyses.

In addition, patients who experience at least one deterioration during the study will be further classified as follows:

- With definitive deterioration: if the deterioration of at least one threshold point as compared to the baseline score is also observed at all time points thereafter (e.g., after the first deterioration is observed) or if the patient dropped out after deterioration, resulting in missing data.
- With transient deterioration: otherwise.

4.2.2. PROMIS FATIGUE 13A SHORT FORM AND SELECTED ITEMS FROM PROMIS FATIGUE BANK, PROMIS INTEREST IN SEXUAL ACTIVITY ITEMS

The PROMIS Fatigue data is collected as a 7-day recall report from patients at Visit 1, 4, 7, 10, and 11.

The scoring manual for PROMIS Fatigue 13a short form can be found online ([Patient-Reported Outcomes Measurement Information System Fatigue scoring manual](#)) (accessed on 16th March 2020).

Each question from the PROMIS Fatigue 13a short form has five response options (1= Not at all, 2=A little bit, 3=Somewhat, 4=Quite a bit, 5=Very much). To use the scoring tables from the PROMIS fatigue scoring manual, a summed score is calculated. The lowest possible summed score is 13 and the highest possible summed score is 65. All questions must be answered in order to produce a valid score using the scoring tables. Once calculated, the total summed raw score is translated to a T-score. The T-score re-scales the

Document: \\ieedc-vnasc01\Sites\ [REDACTED]\NLHOF\IntProjects\Consulting\Projects\ Corvidia\ [REDACTED]
Biostatistics\01.Documentation\02.SAPI Corvidia_RESCUE_PROSAP_v2.0_21JUL2020
Author: [REDACTED] Version No: v.2.0
Template No.: [REDACTED] Version Date: 21JUL2020
Effective Date: 01Dec2018 Reference: [REDACTED]

raw score into a standardized score with a mean of 50 and a standard deviation (SD) of 10. The T-score and standard error are then used to calculate the 95% confidence interval (CI) around the observed score. The 95% CI is calculated as $T\text{-Score} \pm 1.96\text{*SE}$. The T-score will not be calculated if a response is missing for one or more questions from the PROMIS Fatigue 13a short form.

In addition, preliminary scoring of the PROMIS Fatigue 13a includes the calculation of two subdomain scores:

- Symptom score (5 symptom items):
 - I feel fatigued
 - I feel weak all over
 - I feel listless ("washed out")
 - I feel tired
 - I have energy
- Impact score (8 impact items):
 - I have trouble starting things because I'm tired
 - I have trouble finishing things because I'm tired
 - I am able to do my usual activities
 - I need to sleep during the day
 - I am too tired to eat
 - I need help doing usual activities
 - I am frustrated by being too tired to do the things I want to do
 - I have to limit my social activity because I am tired.

The subdomains will be calculated as the sum of the items in the corresponding subdomain. The subdomain score will be calculated only if all items are answered.

Alternative means of scoring, by including also the additional PROMIS Fatigue items from the Item Bank, are described in the PAP and may be derived as follows:

- A total fatigue score summing the items for the PROMIS Fatigue short form 13a and the additional three items from the PROMIS fatigue item bank (de novo 16-item short form)
- Symptom score (8 symptom items):
 - I feel fatigued
 - I feel weak all over
 - I feel listless ("washed out")
 - I feel tired
 - I have energy
 - FATEXP36: How exhausted were you on average?

Document: \\ieedc-vnasc01\Sites\ [REDACTED]\NLHOF\IntProjects\Consulting\Projects\Corvidia\ [REDACTED]
Biostatistics\01.Documentation\02.SAPI\Corvidia_RESCUE_PROSAP_v2.0_21JUL2020
Author: [REDACTED] Version No: v.2.0
Version Date: 21JUL2020
Template No.: [REDACTED] Reference: [REDACTED]
Effective Date: 01Dec2018

- FATEXP43: How physically drained were you on average?
- FATEXP52: To what degree did your fatigue make you feel less alert?

If psychometric analyses support the creation of the latter two domains, clinically meaningful thresholds will also be derived for them, as well as the three standard fatigue scores from the 13-item set.

Given *PROMIS* Fatigue items and *PROMIS* Interest in Sexual Activity item are collected at Week 23 and at Week 24, an assessment will be derived for the hypothesized scores as the mean value of the two assessments at Week 23 and Week 24, which will be labeled as Week 24. In case only one assessment is available, this only assessment will be used as Week 24 assessment.

Change from baseline defined as post-baseline value minus baseline value will be calculated for each assessment. At each post-baseline assessment, the change in scores from baseline will be calculated for each scale/item.

Different domain scores may result from the psychometric analyses described in a separate PAP. In this PAP, clinically meaningful thresholds for these potential domains, as well as the standard one for *PROMIS* fatigue -13a short form will also be derived. Change from baseline in the domain scores that may result from the psychometric analysis will be categorized at each visit as improvement/stable/deterioration using the clinically meaningful threshold value for change scores derived in the psychometric analyses as follows:

- Improvement: a change from baseline \leq -threshold points;
- Deterioration: a change from baseline \geq threshold points
- No change: a change from baseline between (-threshold to threshold).

Sensitivity analyses may be performed if more than one threshold values are suggested by the psychometric analyses.

In addition, patients who experience at least one deterioration during the study will be further classified as follows:

- With definitive deterioration: if the deterioration of at least one-threshold point as compared to the baseline score is also observed at all time points thereafter (e.g., after the first deterioration is observed) or if the patient dropped out after deterioration, resulting in missing data.
- With transient deterioration: otherwise.

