2.4.6. ASSESSMENT SCHEDULE FOR PRO INSTRUMENTS

Patient-reported outcomes will be assessed through a personal device supplied by Corvidia:

- At home daily on patient's personal device: CARES
- At the clinic prior to dosing on patient's personal device: PROMIS Fatigue 13a Short Form and selected items from PROMIS Fatigue item bank, PROMIS Interest in Sexual Activity item, SF-36v2, EQ-5D-5L, PGIC, PGIS.

CARES data will be collected at home on patient's personal device or one provided by Corvidia; the questionnaire will be answered daily for 7 days prior to treatment administration

Document: \\ieedc-vnasc01\Sites\ [REDACTED]\NLHOF\IntProjects\Consulting\Projects\ Corvidia\ [REDACTED]\Biostatistics\01.Documentation\02.SAPI Corvidia_RESCUE_PROSAP_v2.0_21JUL2020
Author: [REDACTED] Version No: v.2.0
Template No.: [REDACTED] Version Date: 21JUL2020
Effective Date: 01Dec2018 Reference: [REDACTED]

(Screening day -7 to day -1 prior to dose 1 (Visit 1), dose 2 (Visit 4), dose 4 (Visit 7), and for the last 2 weeks after dose 6 (Visit 9), i.e. during weeks 23 and 24.

The SF-36v2 and PROMIS Fatigue items will be collected on patients' device at the clinic prior to treatment administration at Visit 1, Visit 4, Visit 7, Visit 10 and 11, or the early termination visit (whichever occurs first).

The PROMIS interest in sexual activity item and EQ-5D-5L will be collected on patients' device at the clinic prior to treatment administration at Visit 1, Visit 4, Visit 7 and Visit 11, or the early termination visit (whichever occurs first).

The PGIC will be collected on patients' device at the clinic prior to treatment administration at Visit 4, Visit 7, and Visit 11, or the early termination visit (whichever occurs first).

The PGIS will be collected at home on patients' devices on the last day of CARES assessment period, i.e. day prior to dose 1 (Visit 1), dose 2 (Visit 4), dose 4 (Visit 7), and at Visit 11, or the early termination visit (whichever occurs first).

The schedule of assessment for all PRO instruments collected in different periods of the study are shown in Table 1.

Table 1 PRO Instruments Assessment Schedule

Study Period	Screening	Treatment											Safety F/Up ^a			
		1	2	3	4	5	6	N/A	7	8	9	10	11/ET ^b	12	13/ET	
Visit Number	-2	-1	1	2	4	5	7	9	12	13	17	21	23	24/ET	28	32/ET
DOSING			X		X		X		X	X	X					
CARES		X		X			X				X	X				
PROMIS			X		X			X			X	X				
Fatigue			X		X			X				X				
PROMIS Sex Item				X				X								
SF-36v2			X		X			X			X	X				

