6.1.1. VARIABLES GENERATED FROM CARES

For each item, weekly scores will be derived as the average of the 7 consecutive daily scores as follows:

Baseline = average of Day -7 to Day -1

Week 5 (Visit 4) = average of Day 22 to Day 28

Week 13 (Visit 7) = average of Day 78 to Day 84

Week 24 (Visit 11) = average of Day 155 to Day 168

For Baseline, Week 5 and Week 13, if more than 3 daily scores out of the 7 days (>50%) within the weekly period are missing, then the score is set to missing.

For Week 24, if more than 7 daily scores out of the 14 days (>50%) within the bi-weekly period

Document : /Users/[REDACTED]/Dropbox (Corvidia Tx)/Corvidia Tx Team Folder/Assets/COR-001/Clinical/RESCUE (COR-001-02)/Manuals & Plans/PRO PAP/Corvidia_RESCUE_PAP_FinalV2.0_24APR2020.docx

Author: [REDACTED] Version No: V2.0

Version Date: 24APR2020

Template No.: [REDACTED] Reference: [REDACTED]

Effective Date: 01Dec2018

Copyright © 2018 [REDACTED] All rights reserved. The contents of this document are confidential and proprietary to [REDACTED] and its subsidiaries. Unauthorized use, disclosure or reproduction is strictly prohibited.

are missing, then the score is set to missing.

Preliminary scoring of the CARES includes the calculation of a Total Symptom Score (TSS). Alternative means of scoring the CARES that are derived from the factor analyses and conceptual considerations may also be defined if supported by the data and if the research team considers these to be plausible and clinically useful alternatives. The following conceptual domains from CARES will be considered: physiological (Short Breath, Swelling, Fatigue, Weakness, Light-headedness, Decreased Appetite, Nausea), psychological (Depression, Concentration, Forgetfulness), pain (Bone / Joints, Nerves, Muscle Cramps), and sensorial (Hand numbness/tingling, Uncomfortable legs, Itching, Dry skin, Dry mouth, Cold) symptoms.

In the preliminary scoring, the daily TSS will be calculated as the average of the 19 daily item scores. A daily TSS score will be calculated if at least 10 out of the 19 items (> 50%) are non-missing. The TSS weekly score will be calculated in the same fashion as the individual items. Higher TSS indicate more symptoms/poorer outcomes.

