2.3.4.4 CARES Corvidia ePRO

The CARES Corvidia ePRO is a new PRO instrument under development (see Appendix D of the protocol). It consists of 19 symptom items, with a 24-hour recall, asking patients to report their worst level of that symptom in the past 24 hours on a numeric rating scale from 0 (no symptom) to 10 (symptom as bad as I can imagine).

Data will be collected at home on subject's personal device or one provided by Corvidia; the questionnaire will be answered daily for 7 days prior to dose (Screening prior to Dose 1 (Visit 1), Dose 2 (Visit 4), Dose 4 (Visit 7), and the last 2 weeks after Dose 6 (Visit 23-24). For each item, weekly scores will be derived as the average of the 7 consecutive daily scores as follows

Baseline = average of Day -7 to Day -1

Visit 4 = average of Day 22 to Day 28

Visit 7 = average of Day 78 to Day 84.

If more than 4 daily scores out of the 7 days (>50%) within the weekly period are missing, then the score is set to missing.

A bi-weekly score (the End of Treatment) will also be derived as the average of Day 155 to Day 168. If more than 8 daily scores out of the 14 days (>50%) within the bi-weekly period are missing, then the score is set to missing.

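### The documents give two unreconciled anchors for the Week 5 and Week 13 CARES diary, and the fixed scoring days are safe under only one of them

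*SAP*

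**What the plan says.** **Scoring days.** PRO SAP v2.0 section 4.2.1 defines "Week 5 (Visit 4) = average of Day 22 to Day 28" and uses Days 78-84 for Week 13. PAP v2.0 section 6.1.1 repeats this ("Week 13 (Visit 7) = average of Day 78 to Day 84"), as does clinical SAP section 2.3.4.4 ("Visit 4 = average of Day 22 to Day 28"). The PRO SAP missing-data rule is: "if more than 3 daily scores out of the 7 days (>50%) within the weekly period are missing, then the score is set to missing". Clinical SAP 2.3.4.4 is looser: "If more than 4 daily scores out of the 7 days (>50%) within the weekly period are missing". SAP addendum section 2.3 voids the week at 4 or more missing days, which agrees with the PRO SAP.

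**Diary tied to the dose.** PRO SAP 2.4.6 says of CARES that "the questionnaire will be answered daily for 7 days prior to treatment administration", naming dose 2 (Visit 4) and dose 4 (Visit 7). It puts PGIS "on the last day of CARES assessment period, i.e. day prior to dose 1 (Visit 1), dose 2 (Visit 4), dose 4 (Visit 7"). PAP 2.4.2, clinical SAP 2.3.4.4 and the first part of footnote 22 to the clinical SAP schedule also use the pre-dose week. The study flow diagram allows Visit 4 on Days 29-35 and Visit 7 on Days 85-91.

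**Diary tied to the calendar.** The later lines of footnote 22 start the Week 5 diary at Visit 3 (Day 22, ±2) and attach the Week 13 diary to no visit. The clinical SAP schedule has a separate Week 12 column, visit number N/A, at Days 78-84. The addendum enters PGIS at the end of Week 4 and the end of Week 12. PAP 7.2.1 counts expected diary entries on Days 22-28 and 78-84.

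**The concern.** The scoring window does not move with the visit, but under PRO SAP 2.4.6 the diary does. A patient who fills in every pre-dose day and is dosed late within the permitted window would then have some entries ignored, or lose the weekly score altogether.

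Change in CARES at Week 13 is a key PRO objective (PRO SAP 1.1). The change from baseline to Visit 7, anchored primarily on PGIS, sets the meaningful-change thresholds (PAP 7.3.8.2), and these feed the responder and time-to-deterioration analyses (PRO SAP 5.7 and 5.8). Under the pre-dose anchor, PGIS is answered the day before the dose. For any dose after Day 29 or Day 85, that day lies outside the days averaged for CARES.

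**Working it through.** **1. Reproduce the plan's windows.** Dosing is every 28 days from Day 1 (PRO SAP 2.3). Dose 2 falls nominally on Day 1 + 28 = 29, and dose 4 on Day 1 + 3 × 28 = 85. The 7 days before are Days 22-28 and 78-84, exactly the scoring windows. The fixed windows are therefore correct for a dose on its nominal day.

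**2. Check the missing rule.** 3/7 = 42.9% and 4/7 = 57.1%. Voiding at more than 3 missing days matches its label of over 50%. The clinical SAP's more than 4 means at least 5/7 = 71.4%, so it does not match the same label.

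**3. Pre-dose anchor.** For a dose k days after Day 29 (or 85), the diary covers the 7 days up to the day before the dose. Usable days = 7 − k, and missing days = k.

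| Dose day (Week 5 / Week 13) | Diary days | Usable | PRO SAP rule (>3 missing) | Clinical SAP rule (>4 missing) |
|---|---|---|---|---|
| 29 / 85 | 22-28 / 78-84 | 7 | scored | scored |
| 30 / 86 | 23-29 / 79-85 | 6 | scored | scored |
| 31 / 87 | 24-30 / 80-86 | 5 | scored | scored |
| 32 / 88 | 25-31 / 81-87 | 4 | scored | scored |
| 33 / 89 | 26-32 / 82-88 | 3 | missing | scored |
| 34 / 90 | 27-33 / 83-89 | 2 | missing | missing |
| 35 / 91 | 28-34 / 84-90 | 1 | missing | missing |

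Under the PRO SAP rule a complete diary is intact on 1 of 7 allowed days, truncated but scored on 3, and voided on 3. PRO SAP Table 2 sets the Week 5 target at Day 35, where 1 of 7 days counts. It sets the Week 13 target at Day 85, where 7 of 7 count.

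**4. Calendar anchor.** A Week 5 diary starting at Visit 3 on Day 20, 21, 22, 23 or 24 overlaps Days 22-28 by 5, 6, 7, 6 or 5 days, so a complete diary is always scored. A Week 13 diary on Days 78-84 overlaps 7 of 7.

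**5. Share affected.** Under the pre-dose anchor, the share of complete diaries voided equals the share of patients dosed on the fifth to seventh allowed day. No document gives that distribution, so these are scenarios only: 5% on each of those days gives 3 × 5% = 15%; 10% on each gives 30%; uniform dosing over the window gives 3/7 = 43%. If every dose fell on Day 29 or 85, or if the calendar anchor holds, the figure is 0%.

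**The case against.** The strongest reply is that the diary ran on calendar days, so the scoring window is the collection window. Much of the operational text supports this: the Week 12 column outside Visit 7, the Visit 3 start, the PGIS timing in the addendum, PAP 6.1.5 relabelling the Week 12 PGIS as Week 13, and PAP 7.2.1 naming Days 22-28 and 78-84 as the days on which entries are expected. On this reading PGIS also falls at the end of the scored Week 13 diary. How the device was triggered may be settled in the protocol or the device specification, which are not shown. This reply stands as far as it goes: the loss is conditional, not established.

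It does not remove the inconsistency. The pre-dose wording is current text in PRO SAP 2.4.6, PAP 2.4.2 and clinical SAP 2.3.4.4. Footnote 22 carries both versions, and its Week 13 line refers to the end of the month of dose 3, which also moves with a dose. Dose 3 is allowed on Days 57-63. The last 7 days of a 28-day month are Days 78-84 after a Day 57 dose, but Days 84-90 after a Day 63 dose, which leaves 1 day of overlap.

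A reader might infer that diaries kept on schedule are being discarded, or that about 43% of scores are lost. The documents support neither. A nominal 28-day schedule matches the windows exactly, and 43% needs both the pre-dose anchor and uniform dose days.

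**Conclusion.** The point holds as an unreconciled definition with a conditional consequence. Two diary anchors stand side by side, and the fixed scoring days fully fit only the calendar anchor or a dose exactly on Day 29 or Day 85. If the pre-dose anchor governs, a complete diary is voided on 3 of the 7 allowed dose days under the PRO SAP rule (2 of 7 under the clinical SAP rule). If the calendar anchor governs, no complete diary is lost, although a Week 5 diary started 1 or 2 days off Day 22 loses that many days from its average. The number of patients affected is unknown.

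A reader might extend the point to Week 24, but no fault is shown there. PRO SAP 2.4.6 places that diary in Weeks 23 and 24, Visits 10 and 11 span Days 155-168, and the score uses Days 155-168.

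**What to change.** 1. Reconcile PRO SAP 2.4.6, PAP 2.4.2, clinical SAP 2.3.4.4 and footnote 22 to one stated diary anchor. Dosing stopped in March 2020, before PRO SAP v2.0 was dated (21 July 2020), so the anchor should be set to what was actually scheduled for patients.
2. In PRO SAP 4.2.1, PAP 6.1.1 and clinical SAP 2.3.4.4, score Week 5 and Week 13 from the 7 days on which the patient's diary was scheduled. For a dose-triggered diary, these are the 7 days ending the day before the actual Visit 4 or Visit 7 dose. For a calendar-triggered diary, they are Days 22-28 and 78-84.
3. Require at least 4 of those 7 days everywhere. This is already the rule in PRO SAP 4.2.1 and addendum 2.3, and it replaces the more-than-4 rule in clinical SAP 2.3.4.4.
4. Leave the Week 24 window at Days 155-168. Re-anchoring it to two weeks after dose 6 would do harm: an allowed Day 147 dose would give Days 161-174, of which 174 − 168 = 6 fall in Table 2's Week 28 window.

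The cost is wording in the three plans and one programming change, with no new data. The downside is that under a dose-triggered diary the scored week varies by up to 6 days between patients. Under a calendar-triggered diary the scores are essentially unchanged.

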2.4.1. CARES CORVIDIA

The CARES Corvidia ePRO - henceforth CARES - is a new PRO instrument under development. It consists of 19 symptom items, with a 24-hour recall, asking patients to report their worst level of that symptom in the past 24 hours on a numeric rating scale from 0 (no symptom) to 10 (symptom as bad as I can imagine).

The symptom items cover physiological (Short Breath, Swelling, Fatigue, Weakness, Light-headedness, Decreased Appetite, Nausea), psychological (Depression, Concentration, Forgetfulness), Pain (Bone / Joints, Nerves, Muscle Cramps) and sensorial (Hand numbness/tingling, Uncomfortable legs, Itching, Dry skin, Dry mouth, Cold) symptoms.

The instrument can be found in Appendix A. CARES.

Document: \\ieedc-vnasc01\Sites\ [REDACTED]\NLHOF\IntProjects\Consulting\Projects\ Corvidia\ [REDACTED]
Biostatistics\01.Documentation\02.SAPI Corvidia_RESCUE_PROSAP_v2.0_21JUL2020
Author: [REDACTED] Version No: v.2.0
Template No.: [REDACTED] Version Date: 21JUL2020
Effective Date: 01Dec2018 Reference: [REDACTED]

Copyright © 2018 [REDACTED] All rights reserved. The contents of this document are confidential and proprietary to [REDACTED] and its subsidiaries. Unauthorized use, disclosure or reproduction is strictly prohibited.

2.4.2. PROMIS FATIGUE 13A SHORT FORM AND SELECTED ITEMS FROM PROMIS FATIGUE BANK, PROMIS INTEREST IN SEXUAL ACTIVITY ITEM

The PROMIS Fatigue 13a short form contains 13 items that assess symptoms and impacts of fatigue. The recall period is 7 days. Each item is rated on a five-point Likert scale ranging from 0 = "not at all" to 4 = "very much". Higher scores in these items indicate worse fatigue, except from items 7 ("I have energy") and 8 ("I am able to do my usual activities") where higher score indicates less fatigue.

In this study, three additional fatigue items were administered for further testing to account for exhaustion, being physically drained, and impact on alertness, concepts that resonated with patients during patient interviews but are not covered in the PROMIS Fatigue 13a short form. Such combination is from now on referred to as PROMIS Fatigue.

A number of scales and subscales can be derived from the PROMIS Fatigue set:

- The original Fatigue 13a scale
- The fatigue scale using the whole PROMIS Fatigue item set (13 + 3 de novo 16-item short form)
- Two subscales within the PROMIS Fatigue 13a scale: 1) symptoms of fatigue; and 2) impacts of fatigue

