7.3.2. ITEM-TO-ITEM CORRELATIONS FOR CARES AND PROMIS FATIGUE ITEMS

The purpose of item-to-item correlation analyses is to evaluate inter-relationships among items to determine the extent and degree of correspondence and discordance between items, and whether those patterns are consistent with hypothesized expectations based on the item content.

Spearman rank correlation coefficient will be calculated using baseline data to examine the inter-relationships among items for CARES (Items 1 to 19) and among *PROMIS Fatigue* Items (Fatigue 13a Items 1 to 13, Fatigue Bank Items FATEXP36, FATEXP43 and FATEXP52).

Correlations greater than 0.4 may provide support for combining items into a multi-item scale. Items with coefficients greater than 0.9 and/or less than 0.1 may be considered for item removal.

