7.3.6.1. Convergent and Divergent Validity

The Spearman Rank correlation coefficient will be used to evaluate convergent and divergent validity. Convergent validity refers to how well constructs that theoretically should be related to each other are observed to be related. Divergent validity can be viewed as the counterpart to convergent validity; it assumes that constructs theoretically unrelated to each other will be observed to be unrelated and will have low correlations.

Correlations between the CARES scores (items, TSS and any other scale/domain score as identified by EFA results) and *PROMIS Fatigue* scores (all scores identified in section 6.1.2) with the SF 36V2, EQ-5D-5L, and PGIS will be examined at Baseline. It is expected that there would be moderate to high correlations between domain and total scores of similar content across the assessments, and low correlations for non-overlapping domains.

PROMis Fatigue items 7 and 8 are keyed in the opposite direction of the remaining items and of those in the other instruments. Accordingly, those items should, regardless of the magnitude, show a negative correlation with other items and instruments.

Moderate Correlations

These are expected for CARES Tiredness (items 1, 2, 3, 4, 5) with the following domains:

- SF-36 v2: VT, GH, PF, RP, PCS, BP, MH , SF, RE, MCS
- EQ-5D-5L: Mobility, Self-care, Usual activities, Pain, Anxiety/Depression
- PGIS

and for CARES Items Gastrointestinal (6, 7) with the following domains:

- SF-36 v2: VT, GH, PF, RP, PCS, BP, MH , SF, RE, MCS
- EQ-5D-5L: Pain, Anxiety/Depression
- PGIS

Document : /Users/[REDACTED]/Dropbox (Corvidia Tx)/Corvidia Tx Team Folder/Assets/COR-001/Clinical/RESCUE (COR-001-02)/Manuals & Plans/PRO
PAP/Corvidia_RESCUE_PAP_FinalV2.0_24APR2020.docx

Author: [REDACTED] Version No: V2.0

Version Date: 24APR2020

Template No.: [REDACTED] Reference: [REDACTED]

Effective Date: 01Dec2018

Copyright © 2018 [REDACTED] All rights reserved. The contents of this document are confidential and proprietary to [REDACTED] and its subsidiaries. Unauthorized use, disclosure or reproduction is strictly prohibited.

and for *PROMIS Fatigue* Items 1 to 4 with:

- SF-36 v2: PF, RP, PCS, MH, RE, VT, MCS
- EQ-5D-5L: Mobility, Self-care, Usual activities, Anxiety/Depression

Low to Moderate Correlations

These are expected for CARES Items Mental Health (8, 9, 10) and Pain (11 12, 13) with the following domains:

- SF-36 v2: VT, GH, PF, RP, PCS, BP, MH , SF, RE, MCS

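### The PROMIS Fatigue subscores and the 16-item total are plain item sums, although items 7 and 8 run in the opposite direction and nothing reverses them

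*SAP*

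**What the plan says.** PRO SAP v2.0 section 2.4.2 describes the 13 fatigue items as worse when higher, except items 7 and 8, "where higher score indicates less fatigue". PAP v2.0 section 7.3.6.1 agrees that "items 7 and 8 are keyed in the opposite direction of the remaining items" and expects them to "show a negative correlation with other items and instruments".

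Section 4.2.2 of the PRO SAP then builds a 5-item Symptom score that contains item 7 and an 8-item Impact score that contains item 8. The rule for both is: "The subdomains will be calculated as the sum of the items in the corresponding subdomain". PAP section 6.1.2 repeats it. The PRO SAP allows two further scores. One is "A total fatigue score summing the items for the PROMIS Fatigue short form 13a and the additional three items". The other is an 8-item Symptom score that again contains item 7 and is given no different rule.

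On coding, section 4.2.2 has "five response options (1= Not at all", rising to 5, and the form in Appendix B prints 1 to 5 in the same order for every item. Section 2.4.2 and PAP section 2.4.1.2 instead describe a 0-4 scale. Neither document contains a reversal instruction.

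**The concern.** A sum is a fatigue score only if all its items point the same way. PRO SAP 4.2.2 classes a change at or above plus the threshold as deterioration and one at or below minus the threshold as improvement, so it presumes that higher is worse. With item 7 unreversed, a patient whose energy rating falls from 5 to 1 moves 4 points towards improvement.

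The Symptom and Impact scores enter the MMRM (5.6), the responder analysis (5.7) and the time-to-deterioration analysis (5.8). Fatigue is part of the key PRO objective in section 1.1. Clinical SAP section 2.3.3 also lists an exploratory endpoint that combines the 13a form with the item-bank items.

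The psychometric work is exposed too. PAP section 7.3.2 says: "Items with coefficients greater than 0.9 and/or less than 0.1 may be considered for item removal". Two items expected to correlate negatively meet the lower limit because of their keying alone, and would also miss the 0.40 item-total criterion in 7.3.4. Section 7.3.2.2 expects correlations above 0.50 across the fatigue items, which cannot hold for unreversed items 7 and 8.

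**Working it through.** **The plan's own figure.** The 13a summed range of 13 to 65 is 13 × 1 and 13 × 5. It reproduces, but it is the same with or without reversal, so it does not show which was meant.

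**Inputs from the documents.** The number of items k and of opposite items m are: 5-item Symptom (5, 1), 8-item Impact (8, 1), 8-item Symptom (8, 1), 16-item total (16, 2).

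**Assumptions, not in the documents.** Every item shifts by the same amount d, with unit item SD and a common inter-item correlation r of 0.3 to 0.7.

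**One patient.** Energy falls from 5 to 1 and the other four symptom items each worsen by one point. The plain sum changes by +4 − 4 = 0. With item 7 reversed, it changes by +4 + 4 = +8.

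**Score from least to most fatigue.**
- 5-item: plain 4×1 + 5 = 9 to 4×5 + 1 = 21; reversed 5 to 25.
- 8-item: plain 7×1 + 5 = 12 to 7×5 + 1 = 36; reversed 8 to 40.
- 16-item: plain 14×1 + 10 = 24 to 14×5 + 2 = 72; reversed 16 to 80.

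**Raw effect.** The correct sum moves by k·d and the plain sum by (k − 2m)·d, so the loss is 2m/k: 2/5 = 40%, 2/8 = 25% and 4/16 = 25%. If the opposite items move f times as much as the others, the loss is 2mf / (k − m + mf):

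| f | 5-item Symptom | 8- and 16-item scores |
|---|---|---|
| 0 | 0% | 0% |
| 0.5 | 22% | 13% |
| 1 | 40% | 25% |
| 1.5 | 55% | 35% |
| 2 | 67% | 44% |

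**Standardized effect.** The variance also shrinks. Var(correct) = k + k(k − 1)r and Var(plain) = k + r[(k − 2m)² − k]. For the 5-item score at r = 0.5 these are 15 and 7. The effect in SD units goes from 5/√15 = 1.291 to 3/√7 = 1.134, a 12% loss.

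| Standardized loss | r = 0.3 | r = 0.5 | r = 0.7 |
|---|---|---|---|
| 5-item Symptom | 20% | 12% | 6% |
| 8-item scores | 8% | 4% | 2% |
| 16-item total | 5% | 2% | 1% |

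**Alpha and distribution-based thresholds at r = 0.5.** Alpha = k/(k − 1) × (1 − k/Var) and SEM = SD × √(1 − alpha), in item-SD units.

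| Score | Alpha | Half-SD | SEM |
|---|---|---|---|
| 5-item Symptom | 0.83 → 0.36 | 1.94 → 1.32 | 1.58 → 2.12 |
| 8-item scores | 0.89 → 0.73 | 3.00 → 2.35 | 2.00 → 2.45 |
| 16-item total | 0.94 → 0.85 | 5.83 → 4.47 | 2.83 → 3.43 |

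The half-SD falls while the SEM rises, so on the 5-item score their order reverses. These two quantities are the distribution-based inputs to the triangulation in PAP section 7.3.8.

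**The case against.** The best defence is that the developer's manual may settle the matter. PAP section 6.1 sends the scoring of each instrument to its manual, and the 13a summed score and T-score are explicitly scored that way. The manual is not at hand, so one cannot rule out that it assigns reversed values to items 7 and 8, or that the ePRO export already holds them. The negative correlations expected in PAP 7.3.6.1 concern item-level data and do not prove how sums would be programmed. This stands as a reason to check the export before recoding. It does not rescue the text: the manual is cited for the 13a summed score and its T-score, whereas the subscores and the 16-item sum have a rule written by the plan itself.

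A reader might infer that a quarter to two fifths of any fatigue effect, or of the power to detect it, is lost. The documents do not support that. The 25% and 40% are raw-point losses under equal shifts and literal programming. The MMRM tests and Hedges' g in section 5.6.1 depend on the standardized effect, which suffers far less.

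Nor are all thresholds spoiled. Un-collapsed PGIS anchor results are primary, and since they are estimated on the same score they shrink with it.

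Item removal is also not automatic. PAP 7.3.1 combines item review with qualitative evaluation, and the team already knows the keying.

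Finally, the 0-4 versus 1-5 conflict is only a constant offset and leaves change scores untouched.

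**Conclusion.** The scoring rule is wrong as written. The documents call items 7 and 8 oppositely keyed and then sum them unreversed into scores for which a rise is read as deterioration.

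With equal item shifts and literal programming, the raw-point effect falls by 40% (5-item Symptom) or 25% (8- and 16-item scores). It could be 0% to 67% if the two items move differently from the rest. The standardized loss is about 1% to 20% for r of 0.3 to 0.7. Alpha is depressed and the two distribution-based thresholds are pushed in opposite directions.

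The reach is limited. The 13a T-score is outside this point, the 16-item total and the 8-item Symptom score are optional in the PRO SAP, and all PRO analyses are exploratory without multiplicity adjustment (PRO SAP 5.1). The hs-CRP primary endpoint is not touched.

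**What to change.** In PRO SAP 4.2.2 and PAP 6.1.2, state that the export has been confirmed to hold unreversed responses on the 1-5 coding. State also that items 7 and 8 are then recoded as 6 minus the response before any sum, item-total correlation or alpha, and before the 0.1 item-removal rule is applied. The confirmation matters because a blind recode would reverse the items twice if the export already stores reversed values. Item-to-item correlations and factor loadings change only in sign, so the raw negative correlations can remain as a data check.

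Align the 0-4 wording in PRO SAP 2.4.2 and PAP 2.4.1.2 with 1-5, since the recode formula depends on it.

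The cost is a sentence or two in each document, one check of the export and one recode in the programs. No new data are needed.
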